## 3.6.2 Off-Study Criteria

- Voluntary participant withdrawal from the study
- Death

Version Date: 04/16/2025

• Non-compliance with study treatment and/or testing, or lost to follow-up, at discretion of PI.

The reason for removing participants from study will be documented in the medical record.

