# 3.1.2 Dose Limiting Toxicity

Dose limiting toxicity (DLT) is defined as all treatment related Grade 3 and greater AEs occurring from the initiation of moxetumomab pasudotox-tdfk therapy to within 30 days after the last dose of moxetumomab pasudotox-tdfk treatment. For example, grade >3 cytokine release syndrome, and failure to complete cycle 1 due to toxicity is considered DLT.

Exceptions to DLT include:

- Hematologic toxicity grade 3, or grade 4 resolving within 4 weeks.
- Hematologic toxicity managed with transfusion and/or other support would not constitute DLT.
- Grade 3-4 lymphopenia, leukopenia, or CD4 reductions.
- Grade 3 gastrointestinal toxicity resolving within 72 hours.

- Transaminase and alkaline phosphates elevations grade 3 resolving within 4 weeks.
- Bilirubin elevations associated with Gilbert's syndrome, i.e. total/direct bilirubin ratio ≥4.
- Electrolyte or mineral abnormalities which are grade 3-4, resolving within 4 weeks.
- Grade 3 proteinuria, and fever
- Lipid elevations grade 3 or grade 4 resolving within 4 weeks
- Grade 3 HUS, including HUS-related grade 1-2 creatinine, will not be considered DLT if it resolves within 2 weeks to grade 0-1 creatinine, and is not associated with significant complications including bleeding or need for dialysis or plasmapheresis.
- Allergic reactions to rituximab/Ruxience prevented by desensitization.
- Dosing of both agents must be delayed for any grade 3-4 infection at least possibly related to either drug, and if not resolved despite a 4-week delay will be considered DLT requiring removal from treatment.
- Other isolated grade 3 laboratory abnormalities (not related to CLS or HUS) without clinical signs or symptoms and not associated with clinical sequalae requiring therapeutic intervention.

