## 3.6 CRITERIA FOR REMOVAL FROM PROTOCOL THERAPY AND OFF STUDY CRITERIA

Prior to removal from the study, effort must be made to have all participants complete a safety visit approximately 28-42 days following the last dose of study therapy.

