## 3.6.1 Criteria for removal from protocol therapy

- Completion of study therapy
- Progressive disease or DLT
- HUS
- Unacceptable toxicities as described on Sections 3.1.2 and 3.3.
- Intercurrent illness or medical circumstances, including uncontrolled infection at the discretion of the primary investigator
- Radiation therapy or other treatment for HCL other than splenectomy
- Voluntary withdrawal from the treatment regimen
- PI determines further treatment on this study is not in participant's best interest
- Participants who are off-treatment but still on-study will be followed as per the schedule in Section 3.4, until they begin alternative therapy or voluntarily withdrawal from follow-up testing. Thereafter, they may be followed on-study for survival and other secondary endpoints.
- Positive pregnancy test

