#### **10.3.2** Evaluable for objective response:

Only those participants who have measurable disease present at baseline, have received at least one cycle of therapy, and have had their disease re-evaluated will be considered evaluable for response. These participants will have their response classified according to the definitions stated below. (Note: Participants who exhibit objective disease progression prior to the end of cycle 1 will also be considered evaluable.)

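### Non-compliance with study treatment can take a participant off study, not just off therapy, at the PI's discretion, which can lose response and duration data for reasons linked to outcome

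*Combined protocol and SAP*

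**What the plan says.** Section 3.6.2 (Off-Study Criteria) has three entries: voluntary withdrawal from the study, death, and "Non-compliance with study treatment and/or testing, or lost to follow-up, at discretion of PI". The reason for removal must be documented. Non-compliance is not defined.

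Section 3.6.1 (removal from protocol therapy) covers most of the ways a participant stops treatment, including "Progressive disease or DLT", HUS, unacceptable toxicity and "Voluntary withdrawal from the treatment regimen". For these the plan states: "Participants who are off-treatment but still on-study will be followed as per the schedule in Section 3.4". No rule says when missed treatment belongs under 3.6.1 and when under 3.6.2.

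Section 10.3.2 counts a participant for response only after at least one cycle and a repeat assessment: those who "have had their disease re-evaluated will be considered evaluable for response". The one stated exception is objective progression before the end of cycle 1. Section 10.4.3 compares MRD-free CR among evaluable participants with the historical 30/64 by Fisher's exact test, and analyses response duration by Kaplan-Meier with no censoring rule.

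**The concern.** Stopping treatment and leaving the study are different events. Section 3.6.1 keeps them apart; the third entry of Section 3.6.2 merges them. The trial is non-randomized and describes no blinding, so the person choosing the label knows the participant's tolerance and response to date.

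Two secondary endpoints are exposed.

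- **MRD-free CR.** Under note 27 of the study calendar (Section 3.4), pre-cycle marrows and scans are at the PI's discretion. The other post-baseline marrows are scheduled at end of treatment (EOT), 6 months later, and at restaging. A participant taken off study before EOT may have no post-baseline marrow and so drop out of the denominator. Nothing in Section 10 says that such a participant counts as a failure.
- **Response duration.** A responder removed for missed treatment or testing stops contributing follow-up. If the removal is related to how that person is doing, the censoring is informative.

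With 26 participants, one or two classifications can matter.

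**Working it through.** **Inputs.** All from Sections 10.2 and 10.4.3: 26 evaluable participants, 64 historical participants with 30 MRD-free CRs, one-sided Fisher's exact test at 2.5%, target rate 80% against 47%, accrual ceiling 30 to cover screen failures and inevaluable participants. No dropout or non-compliance rate is given.

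**Step 1: reproduce the plan's power.** Sum the probabilities of all outcome pairs from Binomial(26, 0.80) and Binomial(64, 0.47) for which the one-sided Fisher p-value is at most 0.025. The result is 79.81%, against the stated 79.8%. The test is therefore read as the plan intends.

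**Step 2: p-values with the observed 30/64 held fixed.** For x MRD-free CRs among n evaluable, p is the upper hypergeometric tail: P(X ≥ x) when n are drawn from n + 64 containing x + 30 successes.

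| Counted in the analysis | Rate | One-sided p | Passes 2.5%? |
|---|---|---|---|
| 18/26 | 69.2% | 0.044 | no |
| 18/25 | 72.0% | 0.028 | no |
| 18/24 | 75.0% | 0.016 | yes |
| 17/26 | 65.4% | 0.086 | no |
| 17/23 | 73.9% | 0.022 | yes |

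The smallest passing counts are 19 of 26, 19 of 25, 18 of 24 and 17 of 23. With 18 MRD-free CRs among 26 treated, losing two participants without MRD-free CR from the denominator changes the result. With 17, it takes three.

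**Step 3: allow for replacement.** The plan aims for 26 evaluable, so an unassessed participant would be replaced. Then 19/26 passes (73.1%, p=0.020). Counting one replaced participant as not MRD-free CR gives 19/27 (70.4%, p=0.033), which fails; 20/27 (p=0.015) would be needed. Replacement restores the number but not the selection.

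**Step 4: error rate if k non-responders are always dropped.** Take a true rate of 47% in both groups, start from 26, and remove k participants without MRD-free CR before testing.

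| k | Chance of a one-sided positive result |
|---|---|
| 0 | 1.5% |
| 1 | 2.4% |
| 2 | 3.5% |
| 3 | 5.4% |
| 4 | 8.4% |

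The nominal 2.5% is exceeded from k = 2. The value of k, and the assumption that everyone removed lacked MRD-free CR, are mine. Steps 2 to 4 also take the two arms as pooled and ignore the interim look at 7 of 9.

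**Step 5: check the DLT side.** The DLT window covers events "occurring from the initiation of moxetumomab pasudotox-tdfk therapy to within 30 days after the last dose of moxetumomab pasudotox-tdfk treatment". Four provisions cover it:

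- Section 8.4.3.2 makes adverse event follow-up mandatory for 30 days after the last dose in those withdrawn from treatment.
- Section 3.6 says that, before removal from study, "effort must be made to have all participants complete a safety visit approximately 28-42 days following the last dose of study therapy".
- Section 10.3.1 makes everyone treated evaluable for toxicity.
- Section 3.1.2 states that "failure to complete cycle 1 due to toxicity is considered DLT".

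Two small gaps remain. The safety visit is best effort and may fall on day 28, two days before the window closes. And an incomplete cycle 1 counts as a DLT only if attributed to toxicity, which a non-compliance label could obscure.

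**The case against.** The strongest defence is that Section 3.6.1 already covers the participants one would worry about. Recognised toxicity, progression, a choice to stop the regimen, and the PI's judgement that further treatment is not in the participant's interest all end therapy only. Section 3.3 tolerates dosing delays of up to 4 months, including for trouble reaching the clinic. Off-study removal is permitted, not required. A poor response already shown by re-evaluation keeps the participant in the denominator even if removal follows. Exclusion of the unassessed comes from Section 10.3.2, so a change to 3.6.2 alone cannot recover someone who refuses testing.

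Most of this stands, and it narrows the point. It does not remove it: the same missed cycles can be labelled as withdrawal from the regimen or as non-compliance, with opposite consequences for follow-up and no rule for choosing. The remark about Section 10.3.2 is right, and it is why the fix must also address the analysis.

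A reader might infer two stronger things that the documents do not support.

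- **That DLT data stop when a participant is removed.** The provisions in Step 5 contradict this. Section 3.1.4 also reports no DLT among 9 participants at 40 mcg/kg with one more to enrol. If that status holds, the primary criterion of at most 2 DLTs in 10 would fail only with several late or missed events.
- **That two or three removals would reverse the efficacy conclusion of the planned analysis.** The 18/24 and 17/23 cases leave out the planned replacement to 26 evaluable, assume every removed participant lacked MRD-free CR, and apply only to results near the cut-off.

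**Conclusion.** The concern holds for the secondary efficacy endpoints. Section 3.6.2 lets an unblinded investigator end outcome collection for non-compliance with treatment, contrary to the principle in Section 3.6.1. The plan does not say how the resulting missing responses are counted or how duration is censored.

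The size is unknown because no removal rate is given. Under worst-case assumptions, a borderline result can change sides with one replaced participant (19/26, p=0.020, against 19/27, p=0.033) or two dropped ones (18/26, p=0.044, against 18/24, p=0.016). A result well clear of the cut-off would not: 21/26 gives p=0.003. The primary safety endpoint is largely protected. This is worth correcting, but it does not undermine the trial.

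**What to change.** 1. Move non-compliance with study treatment from Section 3.6.2 to Section 3.6.1, so that where it applies it ends therapy only and the participant stays on the Section 3.4 schedule. This changes follow-up, not any dosing or treatment rule.
2. Limit off-study reasons to death, withdrawal of consent for follow-up, and documented loss to follow-up. The last may include persistent failure to attend testing after a stated number of contact attempts.
3. In Section 10.4.3, count treated participants with no response assessment as not MRD-free CR, at least in a sensitivity analysis of the comparison with 30/64, and include any who were replaced.
4. State the censoring rule for response duration, and report removals by reason and by response status at removal.

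The cost is a short amendment. The visits are already in the calendar, and participants remain free to withdraw. The downsides are some extra tracking of people who miss visits and a possibly slightly lower reported MRD-free CR rate.

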## 4 CONCOMITANT MEDICATIONS/MEASURES

- Prophylactic measures for renal toxicity, hypvolemia, rituximab/Ruxience toxicity and nausea and vomiting will be administered as described in Section 3.1.4.
- Febrile Neutropenia, which is common in participants before responding to treatment, may require empiric antibiotics, either as an inpatient or outpatient. Hematopoietic growth factors may be used if clinically indicated, for example, if grade 3-4 neutropenia is associated with suspected infection. Fever is also common with rituximab/Ruxience and may be treated symptomatically and with interrupting or with decreasing the infusion rate.
- Symptomatic anemia should be treated with appropriate red blood cell support. Transfusion is generally recommended if the hemoglobin falls below 7g/dL. Platelets are generally given when the platelet count is < 8,000/mm^3 or when there is bleeding.
- Participants receiving rituximab/Ruxience, particularly those with high concentrations of circulating malignant cells, commonly have infusional toxicities including fever, chills, nausea and vomiting, dyspnea, hypotension, and palpitations. Infusional reactions with rituximab/Ruxience have been observed in HCL as well as other malignancies and are best managed by slowing or interrupting the rate of infusion.
- Additional toxicities that may arise will be managed per current evidence-based practice guidelines in consultation with a medically responsible investigator if available.
- Concurrent chemotherapy, radiotherapy, immunotherapy, and biologic therapies for treatment of HCL during the study are not permitted.
- Use of steroids is not routinely recommended to prevent CLS or fever from moxetumomab pasudotox-tdfk; however, secondary prophylaxis for infusion-related reactions with dexamethasone IV or oral may be administered at the investigator's discretion.
- Participants will be informed that NSAIDs (except aspirin) should not be taken from the first dose of the cycle through 7 days after the last dose of the cycle.

#### 5 CORRELATIVE STUDIES FOR RESEARCH

#### **5.1** BIOSPECIMEN COLLECTION

## **5.1.1** Sample Collection Table

Test/assay	Vol	Tube a & Storage	Timing	Location of specimen analysis b
Blood Flow cytometry using TBNK assay	18 cc	3 Na-heparin Room temp		Flow Lab B1B58
BMA flow cytometry	2-5 cc	2 Na-heparin Room temp		Flow Lab B1B58 & [name] Lab
Blood PaxGene	2-3 cc	RNA & DNA tubes, Room temp		Biospecimen Processing Core (BPC)
Serum for biomarkers	2-3 cc	1 SST (red top) -20°C or colder		[name] Lab
Anti-drug antibodies (ADAs)	2 cc	Na-heparin (green top) -20°C or colder	Per Study Calendar	
Urine to test for renal proximal tubule cell damage	2 cc	1 Urine yellow conical 8ml 4°C		
PK	2 cc	1 K 2 -EDTA (lavender top) -20°C or colder		BPC
PK bioassay	4 cc	Na-heparin (green top) -20°C or colder		
Blood PBMC	25 cc	5 Na-heparin Room temp	Baseline	

a. Tubes and media may be substituted based on availability with the permission of the PI or laboratory investigator

**Note:** Samples collected during the course of this study will be stored, tracked, and disposed of as specified in investigator's companion protocol, 10-C-0066, on which all participants will be coenrolled.

## 5.1.2 Biospecimen Sharing on Protocol

We may review the participant's NIH medical records to obtain results of procedures conducted under another protocol in order to minimize repeating procedures/tests.

We may obtain existing identifiable research data and/or biospecimens collected under protocol # 10-C-0066 titled "Collection of Human Samples to Study Hairy Cell and other Leukemias, and to

b. The location of specimen analysis may be adjusted at the time the analyses are performed with the permission of the PI or laboratory investigator

Version Date: 04/16/2025

Develop Recombinant Immunotoxins for Cancer Treatment" to minimize repeating procedures/tests.

We may share identifiable research data and/or biospecimens with protocol # 10-C-0066 titled "Collection of Human Samples to Study Hairy Cell and other Leukemias, and to Develop Recombinant Immunotoxins for Cancer Treatment" to which participants are co-enrolled, in order to minimize repeating procedures/tests.

#### 5.2 PLANNED ANALYSES

Note: Platforms and procedures may be adjusted based upon current technology and/or collaborations in place at the time of actual analyses.

#### 5.2.1 PK of Moxetumomab Pasudotox-tdfk

Concentrations of moxetumomab pasudotox-tdfk will be measured using a validated assay. The PK assay is a sandwich ELISA, where moxetumomab pasudotox-tdfk present in K2EDTA plasma is captured on ELISA plates coated with anti-idiotypic mAb against the CD22-binding domain of moxetumomab pasudotox-tdfk (clone G09.4) and detected with biotinylated monoclonal antibody that binds to the PE38 portion of moxetumomab pasudotox-tdfk (IP-49), followed by addition of streptavidin HRP conjugate and TMB substrate. The color intensity (absorbance measured at 450 nm with wavelength correction set to 650 nm) is proportional to the quantity of moxetumomab pasudotox-tdfk) is measured using the Spectramax plate reader (Molecular Devices, Sunnyvale, CA, US). Concentrations of moxetumomab pasudotox-tdfk in controls and clinical samples are interpolated from the standard curve constructed from moxetumomab pasudotox-tdfk spiked into K2EDTA plasma. If a participant develops any grade of HUS or CLS, or has an ocular event with new abnormality by ophthalmologic examination during study treatment, samples for immunogenicity evaluation will be collected within 24 hours of diagnosis, during the event as clinically indicated (e.g., in order to capture peak intensity of the event, as well as at least one timepoint during the period of improvement), and after resolution of the event.

Draw maximum volume of blood into 2.0 mL of potassium (K2) EDTA (lavender-top-tube) from a separate in-dwelling line that is not used for drug administration.

Tubes will be gently inverted 8-10 times to assure adequate mixing with the anticoagulant within 2 hours after collection. Centrifuge within 2 hours of collection for 10 min at 1100-1300 x g to generate plasma. Transfer plasma into the cryovials and immediately freeze the cryovials upright at -20°C or colder. The procedures for the handling of PK samples will be further detailed in a separate Lab Manual.

## **5.2.2** Evaluation of Immunogenicity

Presence of antidrug antibodies (ADA) against moxetumomab pasudotox-tdfk will be assessed in samples taken from all participants prior to the start of Cycles 1, 2, 3, 5 and 7 and at the end of treatment and 3 and 6 months after the last dose. A validated moxetumomab pasudotox-tdfk specific bridging immunoassay using the Meso Scale Discovery platform will be employed to detect anti-drug antibodies. Positive-negative cut points will be used for detecting the presence of ADA. The cut points will be established by statistical evaluation of drug naive validation samples. Due to pre-existing antibodies, cross-reactive with PE38 domain of moxetumomab pasudotox-tdfk, in drug naïve human samples, cut point establishment will be done using pseudo-negative

Version Date: 04/16/2025

samples where pre-existing signals will be inhibited by drug. Samples determined positive in the ADA bridging assay will subsequently be evaluated in a cell-based neutralization assay. This assay identifies neutralizing ADA (NAb), which has the ability to block moxetumomab pasudotox-tdfk-induced cytotoxicity of the B-cell lymphoma line Raji (ATCC, Manassas, VA) as assessed by adenosine triphosphate production in the cells. Titer levels and the domain specificity of ADAs (anti-CD22-binding domain or anti-PE38 domain) will be determined for participants with positive neutralizing anti-drug antibodies (NAb) and may be determined in participants with negative NAb.

If a participant develops any grade of HUS or CLS, or has an ocular event with new abnormality by ophthalmologic examination during study treatment, samples for immunogenicity evaluation will be collected within 24 hours of diagnosis, during the event as clinically indicated (eg, in order to capture peak intensity of the event, as well as at least one timepoint during the period of improvement), and after resolution of the event.

At each sample collection time, draw maximum volume of blood (4.0 mL) in sodium heparin tube. Immediately after collection, the tube will be gently inverted 8 to 10 times to mix the anticoagulant with the blood sample collected. Centrifuge blood within 2 hours of collection. Centrifuge for 10 min at 1100-1300 x g. Transfer plasma into cryovials and immediately freeze the cryovials upright at -20°C or colder. The procedures for the handling of immunogenicity samples will be further detailed in a separate Lab Manual.

# 5.3 STORAGE, USE, AND SHARING OF SPECIMENS AND DATA (INCLUDING FOR SECONDARY RESEARCH)

# 5.3.1 Sample Tracking and Processing

Samples will be ordered in CRIS and tracked through a Clinical Trial Data Management system. Should a CRIS screen not be available, the CRIS downtime procedures will be followed. Samples will not be sent outside NIH without appropriate approvals and/or agreements, if required.

## **5.3.2** Sample Storage and Disposition

Barcoded samples are stored in barcoded boxes according to stability requirements. Access to stored clinical samples is restricted. Unless other permission obtained, samples are only to be used for research purposes associated with this trial (as per the IRB-approved protocol) by investigators named on the protocol. It is the responsibility of the Principal Investigator to ensure that samples are being used in a manner consistent with IRB approval.

Sample barcodes are linked to participant demographics and limited clinical information. This information will only be provided to investigators listed on this protocol, via registered use of a

Version Date: 04/16/2025

sample tracking database (e.g., Labmatrix). It is critical that the sample remains linked to participant information such as race, age, dates of diagnosis and death, and histological information about the tumor, to correlate results with sample characteristics.

## 5.3.3 Protocol Completion/Secondary Use/Sample Destruction

Any specimens remaining at the completion of the protocol will be stored indefinitely in the conditions described above. The study will remain open so long as sample or data analysis continues. All samples and data from consenting participants will be stored in identifiable format until they are no longer of scientific value or if a participant withdraws consent for their continued use, at which time they will be destroyed.

If, at any time, a participant withdraws from the study and does not wish for their existing samples to be utilized, the individual must provide a written request. Following receipt of this request, the samples will be destroyed or returned to the participant, if so requested. The participant's samples and data will be excluded from future distributions, but those which already been distributed for approved research use will not be able to be retrieved.

The PI will record any loss or unanticipated destruction of samples as a deviation. Reporting will be per the requirements of Section 7.2.

With the permission of the participant, specimens and data collected on this study, identifiable through a code available to the study team, will be stored indefinitely and used for secondary research, including genetic research. Furthermore, the data and/or specimens, may be shared with other investigators in identifiable or coded (code key not available to recipient) format for secondary research. Any investigator conducting secondary research in human subjects will seek either additional regulatory approval or exemption for research as appropriate.

Data will also be shared in public database per the study's data sharing plan in compliance with NIH policies.

In addition, specimens/data may be anonymized and further research, including genetic research, conducted at the site or other institutions without participant consent. Participants will be informed that the possibility for this type of research exists.

